### **Maternal Heart Rate analysis**

Maternal heart rate will be calculated from the maternal ECG as recorded by the PreTel Monitor. These maternal heart rates will be compared with the corresponding maternal heart rates obtained from the gold standard pulse oximeter. Heart rate data will be analyzed in 0.25 second epochs, and the epochs will be analyzed for interpretability and accuracy in an identical manner as the fetal heart rate endpoints 1.1 and 1.2.

The sensitivity for monitoring contractions in subjects without an IUPC placed, modified S, will be analyzed as described for run-in subjects described in Objective 2, endpoint 2.4a. Objective 2. To determine the efficacy of PreTel's fetal monitor against the external standard of care and internal gold standard of fetal monitoring.

### **Fetal Heart Rate analysis**

Fetal heart rate tracings will be analyzed in 1 second epochs.

Endpoint 2.1 – FHR interpretability. “PPA” is positive percent agreement for ECG or Doppler vs gold standard (GS). 2x2 tables for interpretable and uninterpretable data using ECG or Doppler versus FSE will be created. The presence of a “valid” FHR using ECG or Doppler will be tested against a valid FSE (as GS) in each epoch. PPA = percent of epochs with “valid GS reading” that also has a valid reading by ECG or Doppler.

Endpoint 2.2 – FHR accuracy. Bland-Altman difference plots (using epoch values) of test vs gold standard will be created for each subject (hence two plots for each subject). RMS error will be calculated from data for each device. RMS = [average(delta^2)]^0.5. This yields an RMS for each subject for each device, then mean RMS errors will be reported for ECG and Doppler.

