### **1.2. Background**

#### **Fetal monitoring**

Fetal monitoring is the primary method used by obstetricians for moment-to-moment assessment of the health of the fetus. Fetal heart rate and uterine contractions together comprise the two elements of a fetal monitor. Fetal monitors are used in 90% of all deliveries in the United States during labor [1]. Even in the outpatient setting, fetal monitoring is used to assess fetal well-being in pregnancies with common conditions, such as obesity [2]. Fetal monitoring tests are, thus, routinely performed in the outpatient and inpatient settings.

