## **2. STUDY DESIGN**

### **2.1. Overview**

This is an NIH SBIR feasibility and efficacy study. This study seeks to validate the reliability of the PreTel Regional Contraction uEMG/ECG Fetal Monitor in accurately determining contraction and the fetal heart rate. The study also seeks to validate the reliability with which the monitor is able to determine true labor contractions from false labor contractions. The study will achieve these goals by utilizing the PreTel Regional Contraction uEMG/ECG Fetal Monitor concurrently with standard fetal and uterine monitoring prior to and during labor.

Patients will be approached as they present for evaluation of labor in Triage and Labor and Delivery. After obtaining consent, we will have the subject sit, slightly reclining. We will place up to 15 EMG electrode pads over her abdomen, spanning most of the surface of the uterus, plus one ground electrode. The arrangement of the electrodes will be documented. If the patient consents to photo-documentation of the arrangement, then a de-identified photo of the sensor arrangement will be taken and stored electronically. The purpose of the image is to assess the

overall abdominal coverage of all EMG/ECG sensors and the placement of the legacy (traditional) monitors. The photograph may be taken before, during or after the completion of testing, so long as it accurately represents the locations of the area and pad sensors of the study device, and the Toco and Doppler of the legacy devices. Should significant adjustments of the study or legacy recording devices occur, such that the locations change, additional photographs may be taken to provide additional information of sensor locations at different times during testing. If the subject requests that a photograph not be taken, or if there is a technical reason that a photograph cannot be obtained, no photograph will be taken, and the subject will continue as a research subject (i.e. She will not be withdrawn from the study.) Failure to obtain an image will not be considered a breach of protocol and will not be reportable as such.

We will record multichannel EMG signals for 60 minutes for each subject. The subject will be eligible for compensation as outlined in section 10.1.

All health care management decision will be based on the standard obstetrical testing.

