**b) Exclusion Criteria:**

- Twins, triplets and larger number multifetal gestations
- Age less than 18 years
- Humans without a uterus
- Non-English reading and/or speaking
- Significant uterine anomalies such as didelphys or bicornuate uterus (women with small, clinically insignificant anomalies such as uterine fibroids are not excluded).
- Participants cannot be participating in any other research study or protocol regarding uterine contraction monitoring during the same study period as required for our study.
- Known allergy to ECG pad adhesive
- Non-living fetus
- Major fetal malformation
- Fetal distress, or other indications for emergent delivery

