## **8. SUBJECT WITHDRAWALS**

Subjects will be advised in the written informed consent that they have the right to withdraw from the study at any time without prejudice. Subjects may be withdrawn by the investigator if the clinical circumstances require immediate delivery (e.g. non-reassuring fetal heart rate, abruption, etc.). If a subject requires withdrawal by the study investigator, uEMG recording will be stopped at that time and no further data will be collected.

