#### Endpoint 1.2 – FHR accuracy.

Bland-Altman difference plots (using epochs) of ECG v Doppler will be created for each subject. RMS error will be calculated, where  $RMS = [\text{average}(\Delta^2)]^{0.5}$ . This calculation yields an RMS for each subject; a mean RMS error will then be calculated for ECG against Doppler as gold standard. We anticipate finding the fetal heart rate accuracy will equal or exceed the accuracy of Doppler.

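### Endpoint 2.2 gives one all-epoch mean RMS as its group-level fetal heart rate accuracy result, with no figure for agreement when the rate moves away from baseline

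*Combined protocol and SAP*

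**What the plan says.** All references are to the Combined protocol and SAP.

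- **Data.** Section 2.1: "We will record multichannel EMG signals for 60 minutes for each subject". Section 14.2, Objective 2, Fetal Heart Rate analysis: "Fetal heart rate tracings will be analyzed in 1 second epochs".
- **Endpoint 2.2.** ECG and Doppler are each compared with the gold standard, which Endpoint 2.1 identifies as the FSE. The error is "RMS = [average(delta^2)]^0.5", and the summary is: "This yields an RMS for each subject for each device, then mean RMS errors will be reported for ECG and Doppler". A Bland-Altman plot is also made for each woman and each device. No bias, limits of agreement, split by heart rate or rule for reading the plots is given.
- **Endpoint 1.2.** The same formula is used without an FSE: "This calculation yields an RMS for each subject; a mean RMS error will then be calculated for ECG against Doppler as gold standard". This endpoint also states the expectation that ECG accuracy will at least match that of Doppler.
- **Endpoint 2.1.** Missing readings are scored here, as the percentage of valid-FSE epochs in which the device also gives a valid reading.
- **Who is recorded.** Section 3.2 b) excludes "Fetal distress, or other indications for emergent delivery". Section 3.2 a) requires dilation below 3 cm and allows an FSE where clinically indicated. Section 8 permits withdrawal, with recording stopped, when immediate delivery is needed. Section 3.1 a) keeps partial recordings unless consent is withdrawn.

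**The concern.** RMS combines bias and scatter, and it gives every epoch the same weight before squaring. If a woman's rate stays near baseline for most of the hour, her RMS mainly describes baseline jitter. Averaging over women then dilutes the recordings in which the rate changed. The resulting figure cannot show whether a device follows a fall in rate.

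Section 1.2 says of monitoring in general: "Fetal monitoring is the primary method used by obstetricians for moment-to-moment assessment of the health of the fetus". Section 2.1 sets out to validate how reliably this monitor determines the FHR. Contractions receive event-level scoring (Endpoint 2.4a) and a timing measure (Endpoint 2.4b). FHR has no counterpart for decelerations, accelerations or baseline.

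What is at stake is the interpretation of the result. A low mean RMS could be reported as FHR accuracy when it was earned almost entirely near baseline, and the order of ECG and Doppler on that figure could differ from their order during rate changes.

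**Working it through.** **Plan's own figure.** None exists for FHR error, jitter or deceleration frequency. The sample size of 23 in Section 14.1 was not set on FHR accuracy and does not bear on this point.

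**Inputs from the plan.** 60 minutes at 1-second epochs gives 3,600 epochs per full recording. Endpoint 2.2 supplies the RMS formula and the mean over women.

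**Assumed inputs.** Jitter, and the depth, length and frequency of decelerations. Device J follows every change, with jitter s_J. Device M has jitter s_M and holds baseline through decelerations.

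**Formulas.** With k deceleration epochs of constant depth d:
- RMS of J = s_J
- RMS of M in an affected woman = sqrt(s_M² + (k/3600)·d²)
- mean RMS of M = (1 − p)·s_M + p·(RMS in affected women), where p is the share of women affected

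**Case 1: five 30-second, 20-bpm decelerations, p = 0.20, s_M = 2, s_J = 5.**
- k = 150, so M's RMS in affected women is sqrt(4 + (150/3600)·400) = 4.55.
- M's mean is 0.8·2 + 0.2·4.55 = 2.51; J's is 5.0.
- Inside decelerations, M's error is sqrt(4 + 400) = 20.1 bpm and J's is 5.
- M ranks first whenever J's jitter exceeds 2.51.

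**Case 2: three 60-second, 40-bpm decelerations, same jitter.**
- k = 180, so M's RMS in affected women is sqrt(4 + (180/3600)·1600) = 9.17.
- M ranks first until p reaches (5 − 2)/(9.17 − 2) = 0.42.

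**Equal jitter, Case 1 decelerations.**
- 2 against 2: M 2.51, J 2.00.
- 5 against 5: affected women sqrt(25 + 16.67) = 6.45, so M's mean is 0.8·5 + 0.2·6.45 = 5.29; J 5.00.
- J ranks first both times.

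**Range with triangular decelerations** (mean square d²/3), each 60 seconds long, s_M = 2. Entries are M's mean RMS, which is also the jitter J must exceed for the order to reverse.

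| Decelerations in affected women | p = 10% | 25% | 50% | 100% |
|---|---|---|---|---|
| one of 30 bpm | 2.10 | 2.25 | 2.50 | 3.00 |
| three of 30 bpm | 2.24 | 2.59 | 3.18 | 4.36 |
| ten of 40 bpm | 2.76 | 3.91 | 5.82 | 9.64 |

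In simulation (23 women, 200 repeats, 25% chance of three 30-bpm decelerations, jitter 2 against 3), mean RMS was 2.58 for M and 3.00 for J, and M ranked first in 96.5% of repeats. With ten 40-bpm decelerations in every woman and jitter 2 against 5, M never ranked first.

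**Signal loss.** An epoch without a device reading has no difference to square. A device that drops out for a 60-second deceleration takes no RMS penalty, and it loses only 60/3600 = 1.7 percentage points in Endpoint 2.1.

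**The case against.** The case for the plan has four parts.

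- **The plots show the failure.** A missed 40-bpm fall would stand out in a woman's Bland-Altman plot. This is right, so accuracy is not literally reduced to one number. But the plots are made woman by woman, and no rule carries what they show into a result.
- **The illustration depends on unequal jitter.** This is also right. The reversal requires the tracking device to be noisier, and squaring penalises large misses when they are frequent. A reader might infer that mean RMS generally favours a device that smooths away decelerations. The working does not support that.
- **The recordings may not be quiet.** A reader might infer from the entry criteria that nearly all tracings are reassuring. The documents give no such figure. They exclude fetal distress, not decelerations, and they keep the stretch before a withdrawal. Endpoint 2.2 also covers only women with a clinically indicated FSE, whose number and deceleration frequency are not stated. The early-labor entry criterion makes few off-baseline epochs plausible, no more.
- **This is a feasibility study with care based on standard monitoring, and no FHR test or margin is set.** That limits the consequence. It does not supply the missing figure.

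A reader might also infer that Endpoint 1.2 can misrank the two devices. It cannot: Doppler is the reference there and has no error of its own. Its difficulty is a different one. A deceleration that ECG shows and Doppler misses counts as ECG error, so that endpoint cannot show ECG accuracy matching or exceeding Doppler.

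**Conclusion.** The point holds for Endpoint 2.2 in a limited form. Its one group-level accuracy figure is a mean of all-epoch RMS values. It carries no information on direction of error or on agreement away from baseline, and the plots do not fill that gap as planned.

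The order of two devices on that figure can be the reverse of their order during decelerations. This needs two conditions together: off-baseline epochs are few, and the device that follows changes is noisier elsewhere. The 2.51 against 5.0 example shows that this is possible; it does not predict this trial's result. All jitter and deceleration values are assumptions, and the share of off-baseline epochs is not stated.

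For Endpoint 1.2 the conclusion concerns wording only: the result measures agreement between ECG and Doppler. This is a worthwhile correction to the analysis plan. It does not invalidate the study.

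**What to change.** **Endpoint 2.2.** Keep the plots and the overall mean RMS. Add one table, for ECG and for Doppler against the FSE, giving:
- signed bias;
- RMS;
- the percentage of valid-FSE epochs with no device reading, so that signal loss during a rate change is counted.

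Report these separately for epochs within, below and above a band around that recording's median FSE rate. Fix the band width before the data are examined (15 bpm either side would be one illustrative choice). Give the numbers of women and epochs in each group.

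**Conclusions.** Base any statement comparing ECG with Doppler accuracy on these groups as well as the overall figure. If the off-baseline groups hold too few epochs, limit the accuracy conclusion to near-baseline rates.

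**Endpoint 1.2.** Report the result as ECG-Doppler agreement, and remove the expectation that it will show ECG accuracy at or above that of Doppler.

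**Cost.** SAP wording and one tabulation of epochs already collected; no change to procedures or care. Off-baseline estimates will be imprecise, and the accuracy claim may have to be narrowed. A band on 1-second epochs will also mix decelerations with baseline drift and reference artefact, so the table describes agreement by rate group and not detection of individual decelerations.

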### **Contraction analysis**

Endpoint 2.3. Uterine contraction interpretability. A 2x2 table of interpretable/uninterpretable data of EMG vs IUPC will be constructed using 10 second epochs and the PPA determined in the same manner as described in endpoint 2.1 for FHR.

### **14.3. Data and Safety Monitoring**

This study entails no more than minimal risk to the patient and fetus. As such, the study does not need a Data and Safety Monitoring committee. Oversight and monitoring of the conduct of the progress of the study will be the responsibility of the local investigators. Concern for the safety and wellbeing of the patients will be reported to the local investigators who will in turn contact the study Sponsor. Data validity and integrity will be handled by [name] following transfer of the de-identified uEMG data.

Endpoint 2.4a – Uterine contraction sensitivity and accuracy. A table of individual contractions identified by EMG, Toco and IUPC will be generated. Contractions detected by EMG or Toco within +/- 30 seconds of IUPC will be defined as True Positive (TP) detections. False Negative (FN) detections are defined as those contractions not detected by EMG or Toco, but detected by IUPC.

Sensitivity, S, for both EMG and Toco, will be calculated as

$$S(\text{EMG or Toco}) = \frac{\text{TP}}{\text{TP} + \text{FN}}$$

For training purposes, the data on laboring patients using non-invasive methods (i.e., not using IUPC) will be analyzed using a modified calculation for S where Toco positive will be used as a proxy gold standard.

$$\text{Modified S (EMG)} = \frac{\text{EMG positive}}{\text{Toco positive} + \text{apparent FN}}$$

Endpoint 2.4b – Contraction timing accuracy.

$\Delta t$  is a measure of the capability of each method to detect the timing of each contraction compared to gold standard.  $\Delta t$  is defined as the time the contraction peak is detected by EMG or Toco minus the time the peak is detected by IUPC in the corresponding contraction.

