### **First generation EMG/ECG fetal monitors**

Because of these potential benefits, fetal monitors using EMG/ECG technology (including display of maternal heart rate) have been developed. These first-generation devices use traditional, circular ECG pads to record fetal ECG, maternal ECG, and uterine signals. However, ECG pads were specifically designed to record heart signals, and yield only small signals from the uterus. Small signals require a moderate amount of data processing suggesting sub-optimal reliability. Reporting of false positive contractions is a problem with EMG reliability that is not seen with legacy methods, and this creates a problem that clinicians have no experience in accommodating.

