#### Contraction analysis

Whether subjects are in true labor or false labor, or perhaps transitioning into labor, will clinically be uncertain at the time of testing. The EMG data will be analyzed to predict the labor status, then the prediction will be correlated with the subject's outcome. Subjects who subsequently deliver within 24 hours will be considered to have been in labor. Those who deliver after 72 hours or more will be considered to be not-in-labor. Subjects who deliver between 24 and 72 hours will be considered to be transitioning into labor.

Endpoint 1.3 – Contraction analysis. Standard methods for EMG analysis of uterine signals utilizes the power of the EMG signal at each time point. The power values are then mathematically converted to mimic the time-dependent tracing of the Toco. In the PreTel analysis, up to 15 sensors will be distributed across the maternal abdomen to measure uEMG activity at each location. Each sensor will detect uEMG events as a function of time, but the events will not be scaled by power. Instead, the bioelectrical activity of each channel will be converted to an assessment of the presence or absence of a bioelectrical event at each time point and in each location. At each time point, events in all channels will be summed to yield a single time-dependent event tracing. This tracing will be mathematically converted to mimic the time-dependent tracing of the Toco. The PreTel Contraction Analysis software program will perform this analysis.

The PreTel Contraction Analysis will be compared against the Toco/IUPC tracing for sensitivity and specificity.

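### Endpoint 2.4a scores EMG and Toco against IUPC without counting false detections, so its sensitivity rewards frequent firing

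*Combined protocol and SAP*

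**What the plan says.** Endpoint 2.4a is printed under section 14.3 (Data and Safety Monitoring). It opens: "Uterine contraction sensitivity and accuracy. A table of individual contractions identified by EMG, Toco and IUPC will be generated". It then defines a hit, "Contractions detected by EMG or Toco within +/- 30 seconds of IUPC will be defined as True Positive (TP) detections", and a miss, "False Negative (FN) detections are defined as those contractions not detected by EMG or Toco, but detected by IUPC". The only summary is S = TP/(TP + FN), for EMG and for Toco. There is no term for an EMG or Toco detection without an IUPC contraction nearby. The text does not say whether the 30 s window is measured from onset or from peak, or whether matching is one to one.

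Endpoint 2.4b defines the timing error as the time of the peak by EMG or Toco "minus the time the peak is detected by IUPC in the corresponding contraction". It names no summary statistic.

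Two other places bear on this:

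- Section 1.2, on first-generation EMG/ECG monitors: "Reporting of false positive contractions is a problem with EMG reliability that is not seen with legacy methods".
- Endpoint 1.3 in section 14.2: the PreTel analysis "will be compared against the Toco/IUPC tracing for sensitivity and specificity". It does not say what counts as a true negative or a false positive.

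**The concern.** A contraction monitor can fail in two ways: it can miss contractions, or it can report ones that did not happen. Endpoint 2.4a measures the first and is silent on the second, although its title claims accuracy as well as sensitivity. By the protocol's own account, the second failure is the characteristic weakness of EMG and is not seen with legacy methods.

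The silence is therefore not neutral between the two devices. If EMG shows higher S than Toco, the reader cannot tell whether it finds more real contractions or simply reports more events. Section 2.2 hypothesises more accurate contraction reporting, and S alone cannot support that.

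**Working it through.** **Inputs.** The matching window is ±30 s, so 60 s wide (Endpoint 2.4a). Section 14.1 assumes 10 contractions per 60-minute recording; its total reproduces as 23 × 10 = 230. The plan gives no numeric target for Endpoint 2.4, so there is no stated result to reproduce for S itself.

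**1. Blind detector, regular firing.** Let a detector ignore the signal and fire at 30 s, 90 s, …, 3,570 s, which is 60 firings in the hour. Every moment lies within 30 s of a firing, so each IUPC contraction is a TP.

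- S = 10/(10 + 0) = 100%, whatever the contraction pattern.
- Unmatched detections = 60 − 10 = 50 per hour.
- PPV = 10/60 = 16.7%. At assumed rates of 15 and 20 contractions an hour it would be 15/60 = 25% and 20/60 = 33%.

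One-to-one matching does not change S if contractions are more than 60 s apart, because no single firing can then lie within 30 s of two of them.

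**2. Slower regular firing.** For an interval T of at least 60 s, expected S = 60/T: 67% at 90 s, 50% at 120 s and 33% at 180 s.

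**3. Random firing.** With n firings placed at random in 3,600 s, and end effects ignored, S = 1 − (1 − 60/3,600)^n. This gives 0.155, 0.285 and 0.396 for n = 10, 20 and 30. Simulations of 5,000 one-hour recordings per setting gave 0.153–0.154, 0.283–0.287 and 0.393–0.396. At n = 60 the formula gives 0.635 and simulation 0.633. S rises with firing rate throughout, and nothing in Endpoint 2.4a offsets the rise.

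**4. Does specificity in Endpoint 1.3 close the gap?** Take 10 true and 10 false detections in an hour, 10-second epochs (the unit Endpoint 2.3 uses), and real contractions of 60 s each. The 60 s is my assumption; the documents give no duration. Contraction-free time is 3,600 − 600 = 3,000 s, or 300 epochs.

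- If each false detection lasts 60 s: specificity = 1 − 600/3,000 = 0.80.
- If each fills one epoch: specificity = 1 − 10/300 = 0.97.
- PPV = 10/20 = 0.50 in both cases.

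The same number of false contractions thus gives quite different specificities, depending on a unit and duration that the plan does not fix.

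**5. Timing error under chance matching.** If the window is peak to peak and the 2.4b pairs are the 2.4a matches, regular blind firing gives errors uniform on ±30 s. The mean is about 0 and the SD is 60/√12 = 17.3 s (simulated: mean 0.04 s, SD 17.4 s). Random firing at 10 to 30 per hour gave SDs of 16.3 to 17.2 s. A mean alone would not expose such a detector.

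**The case against.** The strongest reply is that sensitivity leaves out false positives by definition, so the formula is standard and not an error. That is right. The endpoint is incomplete rather than miscalculated, but its title promises accuracy too, and nothing under it supplies that.

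Second, the firing-every-minute detector is a worst case; random firing at the contraction rate itself scores only about 0.15. This also stands. The example shows that S carries no penalty; it does not predict how the device will behave.

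Third, this is a pilot without a numeric target for Endpoint 2.4. An IUPC is never required by the study (section 5), so Endpoint 2.4a may rest on few subjects. The planned table would let unmatched detections be counted later. These points lower the severity but do not remove the gap.

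A reader might also infer more than the documents support:

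- *That the whole plan ignores false positives.* Endpoint 1.3 names specificity with IUPC among its comparators, and section 5 plans an EMG–tocometry correlation. The omission is specific to Endpoint 2.4.
- *That specificity is impossible for contractions.* Endpoint 1.3 compares time-dependent tracings built from the presence or absence of events at each time point, so true negatives can exist. The fault is an undefined unit.
- *That timing error is truncated at 30 s, or that one-to-one matching is ruled out.* The text is silent on the landmark and the matching. An onset-based window could admit larger peak differences, and the reference to a corresponding contraction suggests pairing.
- *That Endpoint 2.4b looks unbiased for any detector.* A detector that lags consistently by 15 s would show a mean of +15 s. A mean near zero is expected only when firing is unrelated to the signal.

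**Conclusion.** The concern holds for Endpoint 2.4a. As defined, S cannot separate a good monitor from one that fires too often: blind firing every 60 s gives exactly 100%, with 50 uncounted false detections an hour and PPV of 17%. The 100% follows from the window alone. The false-positive count and PPV rest on the plan's 10 contractions an hour. Because the protocol attributes false positives to EMG and not to legacy methods, the omission can tilt the EMG-versus-Toco comparison towards EMG; the documents do not show by how much. Endpoint 1.3 covers the gap only in part until its unit is defined. The 17.3 s benchmark for timing depends on a peak-to-peak window and on pairing by that window. Severity: should-fix.

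**What to change.** - **Endpoint 2.4a:** define a false positive as an EMG or Toco detection not matched to an IUPC contraction. State one-to-one matching and the landmark for the ±30 s window. Report PPV and false positives per hour beside S, for EMG and Toco alike. PPV and the false-positive rate are the essential part, since a matching rule alone leaves the blind detector at 100% when contractions are over 60 s apart.
- **Endpoint 1.3:** keep specificity, define its epoch, and add PPV.
- **Endpoint 2.4b:** keep the timing error on matched pairs and state the pairing rule. Report SD or RMS with 95% limits as well as the mean. If the window is peak to peak, note that chance matching gives a mean of about 0 and an SD of about 17.3 s. Dropping the 30 s limit is not advised: it leaves the every-minute detector unchanged and would mix missed contractions into timing error.

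The cost is some wording and a few more table columns, drawn from the per-contraction table already planned. The downside is that stated performance may look less favourable.
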